Lay Summary – Complete dentures represent the traditional dental treatment for patients without teeth. However, retention and stability of this type of denture are often lacking, so dental implants are indicated in order to improve the stability of the denture, along with the satisfaction of the patient. Usually, the dental implants are inserted and then a period of 3-6 months is waited before any denture is connected to them. Recent studies have demonstrated that connecting the lower denture to the implants immediately after the implant placement, leads to an improvement in the result, with a social and psychological benefit for the patient. Therefore, the aim of this research project is to evaluate the application of the immediate connections of the implants for the upper dentures. 15-40 patients wearing an upper denture will receive 4 dental implants and the denture will be immediately connected. To simplify the surgical procedure, the implants will be placed without exposing the bone. This surgical technique is called guided surgery. Secondary objective of this research project will be the evaluation of the precision of the implant positioning, using this specific technique. The patients will be followed up for 12 months, for the implant and denture evaluation, as well as the evaluation of patient satisfaction and impact on quality of life through questionnaires.

Study Population – Total number of patients is from a minimum of 15 subjects to a maximum of 40. This research project is aimed at patients who wear a complete maxillary denture and would like to improve its stability with the use of dental implants. Patients will be recruited within WVU dental clinics. Patients identified as potential candidates will be evaluated by the PI and CO-Is. If the patient meets the requirements, the patient will be contacted by the dentist, and PI and Co-Is will be presenting the protocol. The Principal Investigator, Sub-Investigators, and Study Coordinators working closely together to identify potential study participants. If a particular patient is found to meet the inclusion criteria, the PI and or Study Coordinator are alerted so that they may determine eligibility. If eligibility is met, the patient is usually approached by their treating dentist, who may also be the PI or Co-I, and the study introduced during their routine clinic visit.

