Primary Objective – The primary objective of this study is to evaluate radiographically at 6 and 12 months post-loading the performance of the Roxolid™ BLX 3.75 mm implants placed using a flapless guided surgery and immediately loaded with a maxillary overdenture. The outcome will be evaluated using peri-implant, radiographic bone level changes from baseline to 6 and 12 months post implant placement.

Secondary Objective(s) – The secondary objectives include evaluation of:

- Condition of the peri-implant mucosa (pocket depth and bleeding on probing).
- Implant stability quotient (ISQ) at baseline and 12 months
- Implant survival at 6 months and 1 year
- The nature and the frequency of surgical and prosthetic complications
- Patient-centred outcomes (OHIP 14)
- Accuracy of the implant placement (additional CBCT is required)

Study Design & Methodology

General overview

This study will be performed at the WVU School of Dentistry. Total number of patients is from a minimum of 15/20 subjects. Each subject will receive 4 implants. Implants will be placed flapless using a guided surgical protocol and will be immediately loaded by means of a locator retained maxillary overdenture. The study is an Investigator Initiated Project: Straumann accepted to partly sponsor the study, providing some financial support and materials (implants and abutments). Also, study participants will receive \$100 as reimbursement for travel expenses for each of the 3 months, 6 months and 12 months recall visits, (visit 6,7, and 8 as per visit schema) for a total of \$300 .

Pre-treatment procedures

An initial evaluation will be conducted to determine whether a patient meets the study inclusion criteria. This evaluation will include medical history, clinical examination and radiographic examination (OPT). A pre-operative prosthetic evaluation of the existing prostheses will be made to establish their quality and the need for a new set of complete dentures before the implant placement. The maxillary denture will be used as radiographic guide for the pre-treatment CBCT assessment. The tridimensional image obtained with the CBCT will be used for the surgical planning of the implant positioning by means of a dedicated implant planning software (coDiagnostix, Dental Wings Gbmh, Chemniz Germany)) and a stereo-lithographic surgical guide will obtained.

Surgical procedures

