Prosthetic complications

The number and nature of prosthetic complications will be recorded as well as the number and nature of any unplanned visit for each group.

Patient-centered outcomes

Patient centered outcomes will be recorded through the Oral Health Impact Profile (OHIP-14), which is a 14-items questionnaire designed to measure self-reported functional limitation, discomfort and disability attributed to oral conditions (Slade 1997). The OHIP-14 has been shown to be reliable (Slade 1997); sensitive to changes (Locker, Jokovic e Clarke 2004) and it has adequate cross-cultural consistency (Allison, et al. 1999).

Accuracy of the guided system

The Software will compare the actual position of the implants with the pre-surgical planned placement. Difference in angulation and depth will be recorded. A second CBCT will be performed immediately after the surgical placement of the implants.

Target Population & Recruitment Methods

The study population consists of 15-40 patients (15 minimum, 40 maximum), male or female ≥ 21 years of age, requiring 4 implants supported maxillary overdenture. The enrollment of patients will be open to a diverse racial and ethnical backgrounds in order to ensure equitable selection.

Inclusion Criteria – Inclusion criteria include:

- Males and females must be at least ≥ 21 years of age
- Fully edentulous maxilla
- The implant site has to be healed for at least 4 months after extraction
- Wearing complete dentures deemed adequate
- Orthopantomogram available (OPT)
- Adequate amount of bone at least at the 2nd premolar position to house a 3.75 x 10 mm implant
- No bone grafting required
- Implant IT ≥ 20 N/cm

Exclusion Criteria – These are both systemic and local exclusion criteria:

Systemic exclusion criteria

- Conditions requiring chronic routine prophylactic use of antibiotics
- Conditions requiring prolonged use of steroids
- History of leukocyte dysfunction and deficiencies
- Bleeding disorders
- History of neoplastic disease requiring use of radiation or chemotherapy
- Metabolic bone disorders
- Uncontrolled endocrine disorder
- Use of any investigational drug or device within the 30-day period prior to implant surgery
- Smoking more than 10 cigarettes a day
- Alcoholism or drug abuse
- Patient infected with HIV

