Risk – The risks for the participants are represented by the possible complications from the surgical procedure, which may include: implant failure, pain; postoperative discomfort; swelling; restricted mouth opening that may last for several days; bleeding; infection requiring additional treatment; stretching of the corners of the mouth resulting in cracking and/or bruising; change in the occlusion (bite); jaw joint pain; fracture of the jaw; injury to nerve branches; numbness or tingling of the lip, gums, cheek that may last for several months.

Benefit – The advantages of implant rehabilitations for the patients include: improved stability and retention of denture; increased masticatory efficiency; slower rate of bone ridge resorption. In particular, according to a recent prospective study, patient satisfaction significantly increased for implant-supported maxillary dentures compared with old dentures in all seven OHIP parameters (functional limitation, physical pain, psychological discomfort, physical disability, psychological disability, social disability, handicap), as well as for cleaning ability, general satisfaction, ability to speak, comfort, esthetics, and stability (Zembic, Wismeijer 2014). The single patient may not receive any direct benefit from this study. The knowledge gained from this study may eventually benefit others.

Statistical Analysis Plan

Primary outcome variables will test for normal distribution and two-way Paired t test or Student t-test will be used to compare the means. Descriptive statistics will be used to describe patient population. Non-parametric inferential

statics will be used for ordinal/non-parametric data set. The chosen sample size will provide enough power to deliver significant results.

Data Safety Monitoring – Any information that is obtained as a result of this research will be kept as confidential as legally possible. The research records and test results may be subpoenaed by court order or may be inspected by the study sponsor or federal regulatory authorities without your additional consent. In any publications that result from this research, neither name nor any information from which the patients might be identified will be published without their consent.

Safety Monitoring & Unanticipated Event Reporting

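### The placement-accuracy outcome commits to angulation and depth only, so the planned results cannot show lateral error

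*Combined protocol and SAP*

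**What the plan says.** The Lay Summary states the aim: "Secondary objective of this research project will be the evaluation of the precision of the implant positioning". The Secondary Objective(s) list repeats it as "Accuracy of the implant placement (additional CBCT is required".

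Under Outcome variables, the paragraph on accuracy of the guided system describes the method: "The Software will compare the actual position of the implants with the pre-surgical planned placement". It then states what is kept: "Difference in angulation and depth will be recorded". The source of the actual position is also given: "A second CBCT will be performed immediately after the surgical placement of the implants". The visit table in Study Duration & Timeline shows a CBCT at screening and another at implant placement.

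Nothing elsewhere adds to this. Accuracy is missing from the list of dependent variables. The Statistical Analysis Plan names tests for the primary outcome variables and generic non-parametric methods, but no analysis specific to accuracy. The point on the implant from which depth is measured, and the direction in which it is measured, are not defined.

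**The concern.** An implant's position relative to plan has three parts: its tilt, its displacement along the planned axis, and its displacement across that axis (mesio-distal and bucco-palatal). The two named variables cover the first two. The third has no variable, although it is part of what an accuracy objective asks about and the planned 3D scan should contain the information.

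At stake is whether this secondary objective can be answered. A report limited to angle and depth could look favourable while saying nothing about a whole direction of error. If lateral deviation were added after the data had been seen, it would no longer be a prespecified measure.

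**Working it through.** The plan gives no figure for accuracy to reproduce: no expected deviation, threshold or sample-size argument. The check is therefore geometric.

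**Inputs**
- Recorded variables: angulation difference and depth difference (accuracy paragraph under Outcome variables).
- Implant size: 3.75 mm diameter and 10 mm length, taken from the bone-volume inclusion criterion.
- Assumed: depth is displacement along the planned axis. The plan does not define it.
- Assumed: all shift and tilt sizes. The documents give none.

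**Definitions.** Let *u* be the unit vector along the planned axis, *v* the unit vector along the actual axis, and *d* the displacement of a reference point (platform or apex) from plan to actual.
- Angle = arccos(*u*·*v*)
- Depth = *d*·*u*
- Lateral = |*d* − (*d*·*u*)*u*|
- Total 3D = |*d*|

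**Step 1: parallel sideways shift.** Here *v* = *u* and *d* is perpendicular to *u*. So angle = arccos(1) = 0 degrees, depth = 0 mm, and lateral = total 3D = |*d*| at both platform and apex.

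| Shift (mm) | Recorded angle (degrees) | Recorded depth (mm) | Lateral and 3D, platform and apex (mm) |
|---|---|---|---|
| 0.5 | 0 | 0 | 0.5 |
| 1.0 | 0 | 0 | 1.0 |
| 1.5 | 0 | 0 | 1.5 |
| 2.0 | 0 | 0 | 2.0 |
| 3.75 | 0 | 0 | 3.75 |

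The two recorded variables take the same values for each of these implants as for one placed exactly to plan.

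**Step 2: sensitivity to the direction of the shift.** Suppose the planned axis is tilted 20 degrees from vertical and a 1 mm shift is horizontal, so not quite perpendicular to the axis. Depth = 1 × sin 20° = 0.34 mm and lateral = 1 × cos 20° = 0.94 mm. Depth then registers part of the shift, but the 0.94 mm lateral component has no variable.

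**Step 3: can the apex position be recovered from the angle?** For a 10 mm implant tilted 5 degrees about its platform, the apex moves sideways by 10 × sin 5° = 0.87 mm. If the platform has also moved 1 mm sideways in the plane of the tilt, the apex is off by 1 + 0.87 = 1.87 mm when the two errors add, and by 1 − 0.87 = 0.13 mm when they oppose. With depth taken at the platform, all three cases are recorded as 5 degrees and 0 mm. Angle and depth together do not fix the apex position.

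**The case against.** The strongest reply is that the text does not forbid other measures. It says the software compares actual with planned position and then names two differences. The word *only* is not there, and the software may well produce lateral deviation. That is fair as a reading of what is possible. But angle and depth are all that the plan commits to, and a measure that is not named may or may not be reported.

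Several stronger readings are tempting, and the documents do not support them.
- **A displaced implant would be declared perfectly placed.** A reader might infer this from the zeros. The plan defines no accuracy score, threshold or pass/fail rule, so nothing is declared. The implant has zero on the two recorded variables, and no more than that.
- **The recorded values would be wrong.** They would not. An implant 1.2 mm lateral and 0.5 mm deep has a total displacement of √(1.2² + 0.5²) = 1.3 mm, but a recorded depth difference of 0.5 mm is correct as depth. The fault is a missing component.
- **The positional information is thrown away.** It is unrecorded, which is different. Under Confidentiality, collected data are kept for at least 3 years after the project ends. If the scans and planning files are among those data, lateral deviation could still be measured.
- **Large sideways errors are to be expected.** Nothing in the documents shows this. The shift sizes above demonstrate what the variables cannot detect, not what will occur.

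Two further objections stand in part. The zero result depends on how depth is referenced, as Step 2 shows, and the plan leaves that open. This is also a secondary outcome without an analysis of its own, which limits how serious the gap is.

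**Conclusion.** The concern holds in a limited form. The plan commits to two components of placement error and names none for the lateral direction. With depth taken along the planned axis, a shift perpendicular to that axis leaves both recorded variables at zero whatever its size. The secondary objective on accuracy can therefore be answered only in part from the variables named.

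This goes beyond missing detail, because the two named variables miss a whole direction of error. Its practical size in this trial cannot be estimated, since the documents give no expected deviation in any direction. The conclusion rests on rigid-body geometry and on the depth convention stated above. It does not touch the primary bone-level analysis. The change should be made, but the trial's main result does not depend on it.

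**What to change.** Replace the sentence that names the recorded differences with:

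*For each implant, from the planned-versus-actual comparison, record lateral and total 3D deviation at the platform and at the apex, signed depth deviation along the planned axis, and angular deviation.*

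Add accuracy to the list of dependent variables. State in the Statistical Analysis Plan that these measures will be summarised descriptively, allowing for four implants per patient. Naming one of them as the lead measure is optional.

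**Cost.** No extra scan, visit or patient is needed, because the second CBCT and the software comparison are already planned. Six fields replace two, so four are added per implant. At 4 implants per patient and 15 to 40 patients, that is 4 × 4 × 15 = 240 to 4 × 4 × 40 = 640 further values. This assumes that the software can export these measures; the documents do not list its outputs, so this should be confirmed. For patients already treated, the same measures can be taken from stored scans and planning files where these have been kept.

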Study Design – This study will be performed at the WVU School of Dentistry. Total number of patients is from a minimum of 15-40 subjects. Each subject will receive 4 implants. Implants will be placed flapless using a guided surgical protocol and will be immediately loaded by means of a NOVALOC TiN retained maxillary overdenture. The patients will be followed up for 12 months, with a total of at least 8 visits (screening, surgery, 1 week, 2 weeks, 4 weeks, 3 months, 6 months, 12 months).

Study Duration – The estimate start of the study is planned to be June 2018. The enrollment of participants will be performed for 2 years, approximately until June 2020. Data collection and analysis will be concluded in June 2021.

Section II: Design

Background & Significance

Since the first application, implant-supported overdentures have been shown to be a reliable and long-term predictable treatment option for completely edentulous patients in terms of both prosthodontic and implant outcomes (Attard, et al., 2004). Besides providing retention and stability, dental implants assist in reducing the impact of tissue borne edentulous prosthesis and are considered the best option when the patient is not able to acquire new muscular patterns and cope with complete dentures (Mericske-Stern, 1994): it has been reported that implant rehabilitations slow the rate of residual ridge resorption (Adell, et al., 1981), increase the masticatory efficiency (Geertaman, et al., 1994) (Mericske-Stern, 1998) and improve the stability and retention of dentures (Jemt, et al., 1996). Moreover, compared to the conventional removable prosthesis, implant overdentures result in an improvement of the general health-related quality of life, with an evident social and psychological impact for the benefit of the patient (Heydecke, et al., 2003). In particular, according to a recent prospective study, patient satisfaction significantly increased for implant-supported maxillary dentures compared with old dentures in all seven OHIP parameters (functional limitation, physical pain, psychological discomfort, physical disability, psychological disability, social disability, handicap), as well as for cleaning ability, general satisfaction, ability to speak, comfort, esthetics, and stability (Zembic, Wismeijer 2014).

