In order to avoid or limit the need of bone augmentation, reduced diameter implants have been introduced. Narrow implants have been used for different applications, such as limited tooth-to-tooth spacing (Reddy, et al., 2008) (Cordaro, et al., 2006), partially edentulous patients (Barter, et al., 2012) (Romeo, et al., 2006), edentulous mandibles (Flanagan, 2011) and recently also edentulous maxillae (Veltri, et al., 2008) (Hallman, 2001). In particular, a recent study (Cannizzaro, et al., 2007) evaluated the use of reduced diameter implants made of Ti-Zr alloy supporting maxillary overdentures retained with locator abutments: after 12 to 16 months of follow-up, no implants were lost, only one implant showed bone resorption greater than 1.5 mm, with an overall success rate of 97.5% and a survival rate of 100%. In that study, Ti-Zr implants were used, in order to compensate the potential drawback of the reduced diameter titanium implants, that is a lower mechanical strength, with the related risk of fracture, especially at the implant-abutment interface.

During the last decades, particular attention has been focused on the computer-guided and –navigated surgery, with the development of different strategies to transfer the digitally planned implant positions to the patient (Van Assche N, 2012). This methodology has been shown to have numerous advantages: high precision in the implant placement, maximization of bone anchorage to the implant, reduction of surgical time and reduction of patient morbidity (Vercruyssen, et al. 2014). For this reason, nowadays computer-guided surgery is a validated and reliable option for implant placement.

Considered the insufficiency of clinical documentation for immediate loading protocols in maxilla, the aim of this study is to assess the clinical and radiographic performance of Roxolid™ 3.75 mm implants 12 months post-loading supporting a maxillary overdenture, using a flapless guided surgery and an immediate loading protocol.

Objectives

Purpose – The purpose of the study is to evaluate the radiographic, clinical and patient-related outcomes of implant-

WVU+kc Protocol #: 1801929813

PI: [name]

Approved:15-Dec-2021Expires:14-Dec-2022Number:1801929813

retained immediately-loaded maxillary complete dentures..

Null Hypothesis

No difference in the radiographic and clinical parameters between baseline, 6 and 12 months post-operative intervals.

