Patients will be recalled at 1, 2, 4, 12 weeks and 6 months and 12 months after surgery. At the post-operative visit occlusion will be checked, as well as stability and retention of the prostheses and the need for any prosthetic maintenance. Periapical radiographs will be taken at baseline and 6 and 12 months visit by paralleling technique using a Rinn® (Dentsply Rinn, Elgin, Illinois, USA) film holder. The film holder will be indexed on the Locator attachment so that the film position could be reproduced for the follow up radiographs. All patient complaints or any complications resulting from a change in health status from baseline or any implant related complications such as pain, paresthesia or peri-implant infection will be recorded as an adverse event in the CRF and will be monitored until the condition is resolved. OHIP-14 questionnaire will be administered at baseline, at 2 weeks' post-surgery and at 3 months, 6 months and 1 year.

Outcome variables

The following clinical parameters will be considered for treatment evaluation:

Independent Variables

- Patient age
- Patient gender
- Implant length
- Implant position
- Implant insertion torque

Dependent Variables:

- Implant failure/success
- Radiographic bone level change
- Prosthetic complications
- Patient-centered outcomes
- PD
- BoP
- PI (O'Leary 1974)
- KT
- (ISQ analysis)

Implant Failure/Success

The success criteria for the implants will be 1) no radiolucency around the implant, 2) no mobility, 3) no suppuration, pain or ongoing pathologic process. Implant that will not fulfil the success criteria will be considered as failed. The failed implants will be removed and replaced with another implant after 8 weeks of healing of the implant site. The replaced implant will be loaded after 3 months of healing.

Radiographic bone level

Radiographic bone level (RBL) change will be measured on standardized periapical radiographs. A masked examiner will make the bone height measurements. The distance between the implant platform and the most coronal level of the

WVU+kc Protocol #: 1801929813

PI: [name]

Approved:15-Dec-2021Expires:14-Dec-2022Number:1801929813

bone deemed to be in contact with the implant surface will be evaluated. Mesial and distal bone height measurements will be averaged for each implant. The measurements of the bone level at implant placement will be considered as baseline. The RBL change will be calculated in comparison with the baseline value.

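### The primary t-test names no unit of analysis, although bone level change is formed per implant and each patient has four implants

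*Combined protocol and SAP*

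**What the plan says.** The inferential plan is one short paragraph under Statistical Analysis Plan. For the primary outcome it states: "Primary outcome variables will test for normal distribution and two-way Paired t test or Student t-test will be used to compare the means". It mentions no unit of analysis, no averaging within patient and no model or adjustment for clustering, and no other section does.

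Four other places bear on the point:

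- Study Design: "Each subject will receive 4 implants".
- Radiographic bone level: "Mesial and distal bone height measurements will be averaged for each implant". Change from baseline is then calculated, and the text does not go on to combine a patient's implants.
- Primary Objective: "The outcome will be evaluated using peri-implant, radiographic bone level changes from baseline to 6 and 12 months post implant placement". There are thus two primary visits.
- Null Hypothesis: "No difference in the radiographic and clinical parameters between baseline, 6 and 12 months post-operative intervals". This is a comparison over time within one cohort.

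Under Implant Failure/Success the protocol adds: "The failed implants will be removed and replaced with another implant after 8 weeks of healing of the implant site". No section says whether a replacement implant counts in the bone level analysis.

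**The concern.** The last derivation step in the protocol leaves one bone level change per implant, so the natural analysis file has four rows per patient. Running a paired t-test on those rows would follow the plan as written. That test treats the rows as independent. Implants in one mouth share the same host, denture, hygiene and surgeon, so their changes may well be positively correlated. If they are, the test understates the standard error: the p-value is too low, and any interval computed from that standard error is too narrow.

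Two compliant analyses of the same data could therefore report clearly different precision, and the choice between them could be made after the data are seen. The planned number of patients does not limit the problem, because the inflation depends on the number of implants per patient and their correlation.

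The Student option is a smaller matter. The null hypothesis compares visits in the same patients, and an independent-samples test ignores that pairing. The protocol lists possible explanatory variables under Outcome variables and refers to groups under Prosthetic complications, but it defines no groups and links none of these to Student's test.

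**Working it through.** **No planned figure to reproduce.** The plan gives no alpha, power, effect size, standard deviation or ICC, only a statement that the sample size is sufficient.

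**Inputs from the documents.** Implants per patient, m = 4 (Study Design). Patients, N = 15 to 40 (Target Population & Recruitment Methods), hence 4 × 15 = 60 to 4 × 40 = 160 implants. The General overview words the number differently ("Total number of patients is from a minimum of 15/20 subjects"), but N = 20 gives nearly the same error rates.

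**Assumptions.** One two-sided 5% test at one visit; normally distributed changes; equal correlation among a patient's four implants; all implants observed; ICC of the change scores 0, 0.1, 0.2, 0.3 or 0.5.

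**Formulas.**

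- Design effect: DE = 1 + (m − 1) × ICC = 1 + 3 × ICC.
- True standard error ≈ √DE × the implant-level standard error.
- Equivalent number of independent implants = 4N / DE.
- Approximate true type I error of the implant-level test = 2 × [1 − Φ(1.96 / √DE)].

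Example at ICC 0.3: DE = 1 + 3 × 0.3 = 1.9; √DE = 1.378; 60 / 1.9 = 31.6; 1.96 / 1.378 = 1.422, so the error rate is 2 × [1 − Φ(1.422)] = 15.5%.

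The simulated rates below come from 100,000 trials per setting.

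| ICC of change | 0 | 0.1 | 0.2 | 0.3 | 0.5 |
|---|---|---|---|---|---|
| DE | 1.0 | 1.3 | 1.6 | 1.9 | 2.5 |
| Equivalent independent implants, of 60 | 60 | 46.2 | 37.5 | 31.6 | 24 |
| Equivalent independent implants, of 160 | 160 | 123.1 | 100 | 84.2 | 64 |
| Type I error, implants, formula | 5.0% | 8.6% | 12.1% | 15.5% | 21.5% |
| Type I error, implants, simulated, N = 15 | 5.0% | 8.5% | 12.1% | 15.6% | 22.0% |
| Type I error, implants, simulated, N = 40 | 5.0% | 8.5% | 12.1% | 15.5% | 21.6% |
| Type I error, patient means, simulated, N = 15 | 5.0% | 5.0% | 5.0% | 5.0% | 5.2% |
| Type I error, patient means, simulated, N = 40 | 5.0% | 5.0% | 5.0% | 4.9% | 4.9% |
| Interval width, patient means ÷ implants, N = 15 | 1.06 | 1.21 | 1.35 | 1.47 | 1.70 |
| Interval width, patient means ÷ implants, N = 40 | 1.02 | 1.16 | 1.29 | 1.41 | 1.62 |

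**Missing implants.** With 5% or 10% of implants missing at random (assumed), the implant-level error is 8.1–8.4 / 11.4–11.9 / 14.6–15.3 / 20.3–21.4% at ICC 0.1 / 0.2 / 0.3 / 0.5. Patient means stay at 4.7–5.2%.

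**Effect on the estimate.** The mean over implants weights each patient by the number of implants observed; the mean of patient means weights patients equally. The two agree when every patient contributes the same number of implants, whether four or three. Otherwise they may differ.

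**Student's test.** Used for a visit comparison in the same patients, it takes the variance of the difference as 2σ²/N when it is 2σ²(1 − ρ)/N, with ρ the correlation between visits. Simulated rejection under the null at a nominal 5% is about 2% at ρ = 0.3 and 0.1% at ρ = 0.7 (ρ assumed). The fault here is lost power, the opposite of the clustering problem.

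**The case against.** The strongest reply is that the harm is conditional twice over. The plan does not choose implants as the unit, and the sample size is counted in patients throughout, which leans towards a patient-level reading. The ICC is also undocumented, and at 0 the implant-level test holds its 5%. Both points are right. They limit what can be said about the size of the harm but do not remove the omission, because counting patients for recruitment does not define the rows of an analysis.

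A reader might infer that the plan prescribes an implant-level test, or that the trial's type I error is 22%. The documents support neither: they leave the unit open, and 22% belongs to one assumed ICC under one of two permitted analyses. Nor do they say that visits will be compared with Student's test. They offer it as an alternative without assigning it, and gender, listed as an independent variable, would be a possible use.

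It can also be said that type I error matters less here. The study has a single arm, no success margin and no decision tied to the p-value, and the plan promises no confidence interval. That stands and lowers the severity, although a published standard error from 60 to 160 implants treated as independent would still mislead.

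Finally, patient means do not cure loss that depends on the outcome. In an extreme illustration where the 5% of implants with most bone loss go unobserved, the patient-mean test rejects a true zero change in roughly 5.5–12.5% of trials with 15 patients and 8.5–29% with 40, for ICC from 0.5 down to 0. This must be acknowledged whichever unit is used.

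**Conclusion.** The omission is certain: no unit of analysis is stated for the primary test, and the text permits one that ignores clustering of four implants within a patient. The consequence is conditional on implants being tested and on their changes being positively correlated. Over an assumed ICC of 0.1 to 0.5, a nominal 5% test then has a true error of about 8.5% to 22%, and enrolling 40 rather than 15 patients barely changes this. Testing patient means keeps the error near 5% under the same assumptions, and also when some implants are missing at random.

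Student's test does not suit the stated null hypothesis and has no other assigned role; this is a point of clarification.

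The plan should be changed, but with a single arm and no decision rule resting on the p-value the point falls short of a critical defect.

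**What to change.** In the Statistical Analysis Plan, replace the sentence on the t-tests with wording such as:

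> The patient is the unit of analysis for the primary outcome. At each of the 6- and 12-month visits, RBL change from baseline is averaged over the patient's originally placed implants that have a radiograph at that visit. The patient averages are tested with a paired t-test (one-sample on change) and reported with a 95% confidence interval. If 6 and 12 months are also compared, patient means are taken over the implants seen at both visits. The normality check and any non-parametric alternative use the same patient-level values. Replacement implants do not enter the average. Failed implants are reported alongside it, with a note that the mean of surviving implants is biased if loss is related to bone loss.

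Remove Student's test for the time comparisons.

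The cost is SAP wording only, with no added visit or measurement. Compared with an implant-level analysis, the confidence interval is 6% wider at 15 patients and 2% wider at 40 if the ICC is 0. It is about 1.2 to 1.7 times as wide if the ICC is 0.1 to 0.5, and in that range the extra width corrects false precision.
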